3.1 Analysis sets

The following analysis data sets will be used in the analyses:

Full analysis set (FAS): The FAS will include all patients who have received at least one dose of the study drug. The FAS will be the primary set for efficacy analyses.

Safety set (SS): The SS will include all patients who have received at least one dose of the study drug and had at least one post-baseline safety assessment. Any patient who has received a dose of study drug and who has no post-treatment safety data of any kind (i.e., no AE assessment, no vital signs, no ECG, no cardiac imaging, no ECOG performance status, and no laboratory assessment) will be excluded from the SS. Note that the statement 'no AE' is considered as an assessment of AE.

The number and percentage of patients in each analysis sets will be presented.

3.2 Protocol deviations

The complete list of CSR reportable protocol deviations are listed in the data handling plan. CSR reportable protocol deviations will be listed.

3.3 Patient disposition

The FAS analysis set will be used for patient disposition summaries. Following categories will be summarized:

1. Number (%) of patients who are treated
2. Number (%) of patients who are still on treatment
3. Number (%) of patients who discontinued study drug
4. Reasons for discontinuation of study drug
5. Number (%) of patients who consent to be followed for survival follow-up

6. Number (%) of patients who lost to follow-up during survival follow-up period (Note: it is defined as the patients whose last known survival status based on the survival follow-up contact occurred more than 6 months before the cut-off date)

For patients who were screened but did not take the study treatment, a listing with reasons for screen failure will be provided.

3.4 Patient background, demographics and baseline characteristics

Demographic and baseline characteristics data, disease characteristics, medical history, and prior anti-neoplastic therapies are collected at the screening visit. Descriptive summaries and/or listings will be provided. The FAS analysis set will be used for the presentation.

Demographic and baseline characteristics

Demographic characteristic variables include:

- Age (years), age group (<65 and \geq 65; <75 and \geq 75 years)
- Sex (Male, Female)
- Race (White, Black or African American, Asian, Other [including American Indian or Other Alaska Native, Native Hawaiian or Other Pacific Islander, and Other])

Baseline characteristic variables include:

- Height and weight
- ECOG performance status
- Cardiac imaging (Left Ventricular Ejection Fraction [LVEF])

Disease characteristics

Disease characteristic variables include:

- Primary tumor type (**Sponsor adjudicated**)
Note: The tumor type adjudication is made based on the combination of the primary site of tumor with the tumor histology/cytology as collected in the CRFs.
- Time (in months) from initial diagnosis to the first dose of ribociclib
- Time (in months) from date of most recent recurrence/relapse to the first dose of ribociclib
- Presence of B symptoms (for lymphoma patients only)
- Stage at initial diagnosis
- Prior lines of antineoplastic medication therapy
- Prior lines of chemotherapy
- Prior antineoplastic radiotherapy (yes/no)
- Prior antineoplastic surgery (yes/no)

Other patient characteristics

- Gene mutations as detected by local and central labs in pre-defined per-protocol mutation categories

- Age of biopsy samples (in months) calculated from date of biopsy sample date to the first dose of ribociclib

Medical history

Medical history and ongoing conditions, including cancer-related conditions and symptoms will be summarized and listed. The summaries will be presented by primary system organ class and preferred term. Medical history/current medical conditions are coded using the Medical dictionary for regulatory activities (MedDRA) terminology (v18.0). A separate summary will be presented for ongoing medical conditions by severity of the condition (i.e., grade 1 to grade 4).

Prior anti-neoplastic therapies

Prior anti-neoplastic therapies will be listed in three separate listings:

- Medications
- Radiotherapy
- Surgery

3.5 Study Treatment and concomitant medications

The safety set will be used for all analyses associated with study treatment and other medications/non-drug therapy.

3.5.1 Study treatment

Patients receive ribociclib (600 mg) once daily, 3 weeks on and 1 week off. A complete treatment cycle is 28 days. There is no break between dosing cycles. For patients who are unable to tolerate the protocol-specified dosing schedule, dose reductions or interruptions are permitted to manage drug-related toxicities.

- When dose reduction is necessary, the dose of ribociclib may be reduced to 400 mg.
- If an additional dose reduction is required, ribociclib may be reduced to 200 mg.
- Once the ribociclib dose is reduced it cannot be re-escalated.

Protocol Section 6.3 provides the detailed information for dose modifications or dose delays.

3.5.1.1 Duration of exposure

Duration of exposure (days) for study drug is defined as the days between the last ribociclib dose and first ribociclib dose, that is to say, duration of exposure (D1) = (date of last administration of ribociclib) – (date of first administration of ribociclib) + 1. Summary statistics will be displayed for the duration of exposure.

Duration of exposure to study drug will also be categorized into time intervals (< 3 months, 3 – < 6 months, 6 – < 9 months,..., etc.). The number and percentage of patients in each category will be presented.

3.5.1.2 Adjusted duration of exposure

Adjusted duration of exposure (days) for ribociclib (D) is the number of ribociclib dosing days a patient would be expected to have received per protocol, given their duration of exposure to study treatment. Since ribociclib follows a 3 weeks on, 1 week off schedule, the adjusted duration of exposure to ribociclib is the duration of exposure to study treatment minus the planned off days for ribociclib. The adjusted duration of exposure to ribociclib (in days) is therefore $21 \times (\# \text{ completed 28 day cycles}) + \text{minimum of } (21, \text{duration of last incomplete cycle})$. Summary statistics will be displayed.

3.5.1.3 Cumulative dose and average daily dose

Cumulative dose is defined as the total dose actually given during the study treatment exposure. Average daily dose is defined as [cumulative dose (mg) / cumulative dosing days (days)].

The dosing record, as collected in the eCRF, includes planned one week drug breaks, thus cumulative dose calculation will be adjusted according to the 3 weeks on, 1 week off schedule. That is, for each dosing record, the calculated total dose of ribociclib will be the daily ribociclib dose $\times 21 \times (\# \text{ completed 28 day cycles}) + \text{daily ribociclib dose} \times \text{minimum of } (21, \text{duration of last incomplete cycle})$. Since the eCRF does not collect cycle start dates, it will be assumed that a new cycle starts when ribociclib resumes after a temporary interruption.

Cumulative dosing days are calculated based on actual dosing days, excluding both one week drug break and temporary dose interruption.

Cumulative dose and average daily dose will be summarized using descriptive statistics.

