### **7.1.2 Treatment period**

Patients will be treated with ribociclib (600 mg, orally) until disease progression, unacceptable toxicity, death or discontinuation from the study treatment due to any other reason.

For details of safety and efficacy assessments, refer to [Table 7-1](#) and [Section 7.2](#).

- Visits and associated assessments that occur  $\pm$  4 days from the scheduled date (except for cycle 1 Day1 where no visit window is allowed) will not constitute protocol deviations.
- The cycle length is 28 days. Day 1 of subsequent cycles will be calculated from cycle 1, day 1.
- Disease Assessments (per RECIST or appropriate hematological response criteria) must be performed every 8 weeks ( $\pm$ 4 days) after first dose of study drug (Day 1 of every odd cycle), until disease progression or end of treatment, whichever occurs first. The frequency of disease assessment may be reduced to every 12 weeks for patients who have at least 4 post-baseline disease assessments and are clinically stable (except MM patients).
- Laboratory assessments performed as part of the screening evaluations, more than 4 days prior to the first dose of study treatment, must be repeated on the first dosing day.
- [REDACTED]

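### After a dose interruption, the SAP's dose intensity and relative dose intensity put a restarted cycle calendar over an unbroken one, so they are overstated or unchanged and can exceed 100% on same-dose resumption

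*SAP*

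**What the plan says.** The relevant text is in SAP 3.5.1.1 to 3.5.1.4 and protocol 7.1.2.

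- **Duration (SAP 3.5.1.1).** Exposure is "defined as the days between the last ribociclib dose and first ribociclib dose", plus one day. Interruptions are not removed.
- **Denominator (SAP 3.5.1.2).** Adjusted duration is "the number of ribociclib dosing days a patient would be expected to have received per protocol, given their duration of exposure to study treatment". It is derived by one formula: 21 days for each full 28-day cycle, plus at most 21 days for a single final partial cycle. The section summarises this by saying that "the adjusted duration of exposure to ribociclib is the duration of exposure to study treatment minus the planned off days for ribociclib". It mentions no restart.
- **Numerator (SAP 3.5.1.3).** Cumulative dose applies the same formula to each dosing record separately. Two reasons are given: "The dosing record, as collected in the eCRF, includes planned one week drug breaks", and no cycle dates are available ("Since the eCRF does not collect cycle start dates"). Hence "it will be assumed that a new cycle starts when ribociclib resumes after a temporary interruption".
- **Ratio (SAP 3.5.1.4).** DI is cumulative dose over adjusted duration, and RDI is DI divided by 600 mg/day.
- **Protocol 7.1.2.** "Day 1 of subsequent cycles will be calculated from cycle 1, day 1".

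**The concern.** A ratio of dose received to dose expected makes sense only if both parts agree on which days were dosing days. Here each resumption gives the numerator a fresh allowance of up to 21 on-days, while the denominator keeps counting the planned off-weeks from C1D1. Planned off-days can then be credited as doses given, or a missed week can disappear.

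The patients affected are those with interruptions, for whom RDI is meant to show how much drug was lost. A value at or above 100% in such a patient would be read as full or excess dosing.

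**Working it through.** **Inputs.** The schedule is 21 days on and 7 off, and planned dose intensity is 600 mg/day (SAP 3.5.1.4). An interruption means 0 mg on a day outside the planned off-week (SAP 3.5.1.5). An interruption for toxicity may last up to 21 days (protocol 6.3.2). For a span of n days the SAP formula is

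A(n) = 21 × floor(n/28) + min(21, n mod 28).

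With one interruption and the same dose throughout:

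- SAP RDI = [A(days before the hold) + A(days from resumption to last dose)] / A(first to last dose)
- C1D1 on both sides = dosed days falling on cycle Days 1-21 counted from C1D1 / A(first to last dose)
- Restart on both sides = credited on-days / (credited on-days + interrupted on-days)

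**Baseline.** The SAP gives no worked DI or RDI. For an uninterrupted patient, A(n) equals the planned on-days for every n from 1 to 799, so DI is 600 mg/day and RDI is 100%, as the SAP intends. The discrepancy arises only after an interruption.

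**Cases at 600 mg throughout.**

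1. Dosed Days 1-10, held 11-13, resumed Day 14, last dose Day 35. Numerator: A(10) + A(22) = 10 + 21 = 31. Denominator: A(35) = 21 + 7 = 28. RDI is 31/28 = 110.7%. On the C1D1 calendar the dosed days are 10 + 8 + 7 = 25, giving 25/28 = 89.3%. Cumulative dose is 31 × 600 = 18,600 mg against 25 × 600 = 15,000 mg.
2. Same hold, last dose Day 34: SAP 31/27 = 114.8%; C1D1 24/27 = 88.9%; restart on both sides 31/(31 + 3) = 91.2%.
3. Same hold, last dose Day 49: 39/42 = 92.9% on all three, so no error.
4. Dosed Days 1-21, planned week off, resumed a week late on Day 36, last dose Day 56: SAP 42/42 = 100%; restart on both sides 42/49 = 85.7%; C1D1 35/42 = 83.3%.
5. Held Day 8 only, last dose Day 29: SAP 28/22 = 127.3%; C1D1 21/22 = 95.5%. This is the largest RDI found.

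**Case 1 with resumption at 400 mg.** SAP: (10 × 600 + 21 × 400)/(28 × 600) = 14,400/16,800 = 85.7%. C1D1: (10 × 600 + 15 × 400)/16,800 = 12,000/16,800 = 71.4%. RDI is below 100% but still 14.3 points too high.

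**Direction.** A(n) is the largest number of on-days that any n-day window can hold on a 21/7 schedule (checked for n = 1 to 199). So the restarted numerator cannot fall below the C1D1 count over the same denominator. By the same fact, the unbroken denominator cannot exceed the sum of the restarted segments under the same numerator. A check of 200,000 random two-hold patterns also found no negative error on either calendar.

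**Grid against the C1D1 calendar.** The grid takes every single hold of 1-21 days that starts on an on-day in cycles 1-2 after at least one dose and ends with resumption on an on-day. The last dose falls on any C1D1 on-day up to Day 168, which gives 59,395 patterns.

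| | Resumed at 600 mg | Resumed at 400 mg |
|---|---|---|
| No error | 57% | 57% |
| Range of error (points) | 0 to +31.8 | 0 to +21.2 |
| RDI above 100% | 6,984 (11.8%) | 144 (0.24%) |

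At 600 mg the median error among the 43% with any error is 7.0 points (interquartile range 4.2 to 10.6). The largest error is 31.8 points with last dose by Day 56, 16.3 for Days 57-112 and 8.2 for Days 113-168.

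**Patients who really restart the cycle.** The same holds, with the last dose on an on-day of the restarted calendar, give 62,902 patterns. At 600 mg, SAP RDI minus restart on both sides runs from 0 to +32.1 points and is zero in 50%.

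**The case against.** **The restart is a disclosed workaround, and SAP 3.5.1.2 may have been meant to share it.** The first half stands: the SAP openly gives the missing cycle dates as its reason, and the assumption is not an error in itself. The second half is possible, since both sections count completed cycles. But 3.5.1.2 does not say so, and one formula with a single partial cycle over the total span does not fit that reading. Two programmers could reasonably produce different RDIs.

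**The figures above 100% depend on the dose at resumption.** This stands. Protocol 6.3.3 resumes some patients at the same dose and others at a lower level, and at 400 mg such values almost vanish. The overstatement does not.

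**The grid is not a population.** This also stands. A reader might infer that about one patient in eight would show RDI above 100%. The documents do not support that. The patterns are unweighted, the shares change with how the grid is built, and the 11.8% assumes same-dose resumption.

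**Average daily dose.** A reader might infer that it is inflated too. Its divisor is described thus: "Cumulative dosing days are calculated based on actual dosing days, excluding both one week drug break and temporary dose interruption". If those days are derived by the restart rule, case 1 gives 18,600/31 = 600 mg/day and nothing is wrong. Only if they come from the C1D1 calendar would it give 18,600/25 = 744 mg/day. The SAP does not settle which applies.

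**Any single calendar is wrong for someone.** True. The gain is internal consistency and a 100% ceiling, not exactness for each patient.

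**Conclusion.** The formulas as written are inconsistent. After an interruption, DI and RDI are overstated or unchanged, never understated, whichever calendar is taken as the reference. In more than half of the grid patterns measured against C1D1 there is no error. Where there is one, it is typically several points, and it can exceed 30 points when exposure is short and the dose is unchanged. Values above 100% despite missed doses are possible with same-dose resumption and rare with reduction to 400 mg.

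The sizes rest on single holds of 1-21 days in the first two cycles, exposure to Day 168, and the reading that 3.5.1.2 has no restart.

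The effect is confined to the descriptive cumulative dose, DI and RDI summaries, and to average daily dose only under the condition described above. A reader might infer that efficacy results or the counts of patients with interruptions and reductions are compromised. They are not, because none of them uses these quantities. The correction should still be made: it is cheap, and the error flatters drug delivery in the patients whose dosing was disrupted.

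**What to change.** Use one cycle calendar for numerator and denominator in SAP 3.5.1.2 to 3.5.1.4, the same for all patients, and state it in each section.

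- **Simplest option.** Keep the restart assumption, since the eCRF holds no cycle start dates, and compute the denominator on the same restarted segments as credited on-days plus interrupted on-days. Case 2 becomes 31/34 = 91.2%.
- **Alternative.** Anchor both sides at C1D1, as in protocol 7.1.2, and delete the restart assumption. Case 1 becomes 25/28 = 89.3%.

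Under either option, derive cumulative dosing days by the same rule, state that a dose change without a gap does not open a new cycle in this calculation, and treat any RDI above 100% as a data or programming query.

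The cost is SAP wording and a small programming change. Reported RDI falls for some interrupted patients, and cumulative dose also falls under the alternative. Some error remains. At 600 mg, the first option still overstates RDI by 0 to 20.8 points on the grid (median 0, 95th percentile 2.5) for patients who kept the C1D1 calendar. The alternative understates it by 0 to 22.6 points for patients who truly restarted; in case 4 it counts 35 doses instead of 42. Neither can exceed 100%.

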3.5.1.4 Dose intensity and relative dose intensity

Dose intensity (DI) will be calculated as follows:

$$\text{DI} = \text{Cumulative dose (mg)} / \text{Adjusted duration of exposure (days)}$$

Planned dose intensity (PDI) is the assigned dose by unit of time planned to be given to patients as per protocol. The planned dose intensity for ribociclib during the period of time the patient received drug is 600 mg/day.

$$\text{RDI} = \text{DI (mg/day)} / 600 \text{ mg/day.}$$

DI and RDI will be summarized using descriptive statistics.

3.5.1.5 Dose interruption and dose reduction

Dose interruption: An interruption is defined as a 0 mg dose given on one or more days during the treatment period where a patient is not on the “off” part of a treatment cycle. For patients who have dose interruption checked but never resume the non-zero dose, the dose interruption will not be counted.

Dose reduction: A reduction is defined as a decrease in dose from the protocol planned dose or a decrease from the previous non-zero dose, during the dosing period, even if this decrease has been directly preceded by an interruption. For example, in the sequence 600 mg – 0 mg –

400 mg, the 400 mg dose will be counted as a reduction; in the sequence 400 mg – 0 mg – 400 mg, the 400 mg dose will not be counted as a reduction.

The number and percentage of patients who have dose reductions or interruptions, and the reasons for such reductions/interruptions, will be summarized separately.

3.5.2 Concomitant medications/non-drug therapies

In general, concomitant medications and therapies deemed necessary for the care of the patient are permitted (see Protocol Section 6.4.1), except as specifically prohibited (see Protocol Section 6.4.2). All medications, procedures and significant non-drug therapies (including physical therapy and blood transfusions) administered within 30 days prior to the administration of ribociclib and through 30 days after the last dose of study drug will be recorded in the corresponding eCRF page.

Concomitant therapy is defined as all interventions (therapeutic treatments and procedures) besides the study treatment that were administered to a patient, preceding or coinciding with the study assessment period.

Concomitant medications entered into the database will be coded using the World Health Organization (WHO) Drug Reference List to allow for categorization by preferred term. In addition to categorizing medication data by preferred term, drugs will be classified according to their ATC classification in order to present and compare how they are being utilized. Non-drug therapies will be coded using the MedDRA terminology (v18.0).

Concomitant medications taken concurrently with the study drugs will be listed and summarized by ATC class, preferred term by means of frequency counts and percentages. These summaries will include medications starting on or after the start of study treatment but no later than 30 days after last dose of study treatment or medications starting prior to the start of study treatment and continuing after the start of study treatment. Similarly, significant non-drug therapies will be summarized by primary system organ class (SOC) and preferred term.

Any prior medications or significant non-drug therapies starting and ending prior to the start of study treatment or starting more than 30 days after the last date of study treatment will be listed.

The safety set will be used for all concomitant medication/non-drug therapy tables and listings.

4 Efficacy evaluation

All efficacy analyses will be performed in FAS.

4.1 Clinical Benefit Rate (CBR)

Clinical benefit is determined by investigator assessment for each tumor assessment and is defined as responses of CR or PR or SD for ≥ 16 weeks. In addition to tumor-specific measurements (e.g., radiological assessment of tumor response for solid tumors), progressive disease will also be considered when it was indicated either as a reason for the study treatment

discontinuation or as a cause of on-treatment death. CR and PR (for solid tumors) require a confirmation that is at least a minimum of 4 weeks after the initial observation of response. Patients who had confirmed CR/PR or SD prior to 16 weeks, but discontinued prior to 16 weeks for reasons other than progressive disease, will have their clinical benefit defined as non-evaluable; patients who had confirmed CR/PR or SD prior to 16 weeks, but progressed prior to 16 weeks, will be considered as not achieving clinical benefit; patients who had CR/PR/SD occurred prior to 16 weeks, but progressed at or after 16 weeks without evidence of CR/PR/SD at or after 16 weeks, will also be considered as not achieving clinical benefit. CBR will be analyzed by comparing achieved CBR with a historical control rate of each tumor type, and if there is at least 80% probability that the response rate in a tumor type exceeds the historical rate, then the tumor type will be considered a success. Details for the Bayesian analyses of CBR are located in Section 8.

In addition to the Bayesian analyses, with all solid tumor types combined and separately for each hematological tumor type, the CBR estimate will be provided with its 95% exact CI. For tumor types (within the solid tumors) that have ten (10) or more patients, separate summaries will be performed by the tumor type. In the event that there are fewer than 4 patients for a hematological tumor type, only listing will be provided for that tumor type.

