2.2 General overview of statistical methodology

Data from all centers that participate in this protocol will be used. Data used for the analyses specified in this document will come from the Electronic Data Capture (EDC) system. In addition, the mutation data from the central laboratory will be collected in an Excel spreadsheet format and subsequently be uploaded to a secure FTP site by Novartis.

The analyses stated in this document will be based on all patients' data up to the time when all patients have had the opportunity to complete at least 4 cycles (or 16 weeks) of study treatment or discontinued study. The data cut-off date will be the date when the last patient on treatment completes 4 cycles of study treatment. This will be the cut-off point for the clinical study report (CSR). Additional data for patients continuing to receive study treatment beyond the data cut-off date for the primary CSR will be reported once all patients have discontinued treatment or been lost to follow-up.

All statistical analyses presented in this document are related to patient background information, efficacy, and safety. All analyses are descriptive and no hypothesis testing is planned (except for the primary efficacy variable, which is described in Section 8 below). For continuous data, the mean, standard deviation (SD), median, 25th and 75th percentiles, minimum, and maximum will be presented. For categorical data, frequencies and percentages will be presented. In general, data from all centers will be combined for any analysis. There will be no stratification factor considered for the analysis with the exception of tumor type in the primary efficacy variable analyses. Missing data will not be imputed. All data collected in the study will be presented in the listings.

The primary efficacy objectives of the study, clinical benefit (e.g., for solid tumor – CR, PR, stable disease [SD] \geq 16 weeks) associated with ribociclib treatment based on local investigator assessment, will be analyzed by using a Bayesian hierarchical model for evaluation of trial success and futility, and the relationship between pathway activation and response (if applicable). Analysis details are documented in Section 8.

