2.3 Change in planned analyses from the protocol

Cardiac imaging is only collected post baseline where clinically indicated and the value and potential abnormality will only be listed, and not summarized.

Summaries will be conducted for all patients combined with the following exceptions –

- Primary efficacy analysis on the clinical benefit via Bayesian hierarchical model
- Other clinical benefit and tumor response summaries for tumor types that have 10 or more patients enrolled.

In the event of a low response rate, DOR will be listed only.

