4.2 Overall Response Rate (ORR)

Overall response is determined by investigator assessment for each tumor assessment in the study. For patients with solid tumors, the assessment criteria will be RECIST 1.1 and will include responses of CR and/or PR. For hematological tumors, other appropriate criteria (see Protocol Appendix section for corresponding criteria) will be used to determine the responses. Ninety-five percent (95%) exact CI will also be provided for the response rates. The number and percentage of patients for different categories of overall response (e.g., for solid tumor - CR, PR, SD, PD, and NE) will be presented. These analyses will be performed with all solid tumor types combined and separately for each hematological tumor type. For tumor types that have ten (10) or more patients (within the solid tumors), separate summaries will be performed by the tumor type. In the event that there are fewer than 4 patients for a hematological tumor type, only listing will be provided for that tumor type.

Components of tumor assessments (target lesion response, non-target lesion response, new lesion [yes/no]) will be listed. In addition, Cancer Antigen-125 (CA-125) in the assessment of ovarian cancer response, or Prostate-specific antigen (PSA) in the assessment of prostate cancer response will also be listed.

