8.1.2 Trial Logistics

The trial will enroll all available patients in all cohorts for 2 years unless a cohort cap is reached or a cohort is stopped early, or the trial is stopped early by Novartis. The trial will enroll no more than 30 evaluable patients in each cohort. Interim monitoring will be conducted starting after the first 30 patients are enrolled overall (across all cohorts), and continuing each 13 weeks thereafter till study enrollment closure. After that, one CBR analysis will be done at the end of the study. At each interim data review, response information for the various groups will be evaluated to determine the current $\Pr(\theta_g > 0 | \text{data})$ within each cohort, with sufficiently high/low values used to stop the cohort for success/futility. A minimum of 10 patients will be required in a cohort before it may discontinue enrollment for futility, and a minimum of 15 patients are required before discontinuing a cohort for efficacy. If a cohort stops enrolling early, the remaining cohorts will continue until the end of 2 years or until the other groups reach their own early stopping criteria. The final analysis will occur after the analysis of the study data for the primary CSR.

The trial will enroll patients in all listed cohorts. In addition, should other cohorts be identified throughout the trial, the following mechanism will be used. If another cohort is identified, it will not be placed into the statistical analysis unless 3 patients enroll within the cohort (thus, the trial may enroll multiple possible cohorts within the “other” category, but a cohort will only be added to the list if at least 3 patients enroll from that cohort). Thus, it is possible (but not viewed as likely) that multiple additional cohorts may be added to the trial if the trial has sufficient enrollment in multiple additional cohorts. In addition to sufficient enrollment, the sponsor must have a reasonable estimate of the control clinical benefit rate.

Patients within any cohort which does not reach the minimum 3 patient enrollment will be excluded from the interim and final analyses. As the study continues, early interim data reviews may be based on fewer cohorts than later interim data reviews, as the interim data reviews will include whatever cohorts have satisfied the criteria at the time of the data review.

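### Patients with SD or a confirmed response who stop before week 16 without progression are non-evaluable for clinical benefit, an undeclared departure from the protocol with no coding given in the primary Bayesian model

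*SAP*

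**What the plan says.** SAP 4.1 sorts patients with an early SD or response into classes. Those with SD or confirmed CR/PR who "discontinued prior to 16 weeks for reasons other than progressive disease, will have their clinical benefit defined as non-evaluable" form one class. Those with the same early result "but progressed prior to 16 weeks, will be considered as not achieving clinical benefit". A third group, progressing at or after week 16 with no evidence of response or SD from week 16 on, is also counted as failing. The section then applies the result to the decision rule: "CBR will be analyzed by comparing achieved CBR with a historical control rate of each tumor type", with success at a posterior probability of 0.80. It refers to Section 8 for details.

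Section 8 defines Y_i only as a response indicator. It uses evaluable without defining it ("The trial will enroll no more than 30 evaluable patients in each cohort"), and counts the minimum of 10 for futility by patients evaluated for response. The only exclusion it states is of cohorts with fewer than 3 patients. Its simulation assumes no dropouts.

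The general text points both ways. SAP Section 4 opens with "All efficacy analyses will be performed in FAS", but SAP 2.2 says "Missing data will not be imputed".

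Protocol 10.4.1 defines CBR, for solid tumours, as CR, PR, or SD of at least 16 weeks. Protocol 10.1.1 assigns efficacy to the FAS. Neither has a non-evaluable class, and protocol 10.4.4 on missing values covers only PFS and OS. SAP 2.3, headed "Change in planned analyses from the protocol", lists cardiac imaging, pooling of summaries and DOR listings. It does not mention this rule.

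**The concern.** The success rule compares each cohort with a fixed outside rate, so numerator, denominator and R_g must be on one basis. The SAP gives neighbouring patient types a failure value and withholds a value from this one. The same patient is then a failure (SD only) or a success (confirmed CR/PR) under protocol 10.4.1, and neither under SAP 4.1.

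Two analysts could follow this SAP and reach different calls on the same data. That could happen here: SAP Section 1 gives the Bayesian CBR analysis to one CRO and everything else to another. The exact confidence interval for CBR in SAP 4.1 also has no stated denominator. Because the simulation had no dropouts, the published operating characteristics do not show the effect of either coding.

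**Working it through.** **1. Model and check against the plan.** Inputs are from SAP 8.4.1 and 8.5: the eight example cohorts and their R_g, Dirichlet process with α = 2, μ ~ N(0, variance 1.82), τ² ~ IG(3, 0.5), Poisson accrual with mean 10 or 5, cap 30, success if Pr(θ_g > 0 | data) > 0.80. Reading 1.82 as a variance is an assumption. The posterior was summed exactly over all partitions of the eight cohorts, with quadrature over μ, τ and θ.

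| Accrual | Scenario | SAP Tables 2.1/2.2 | Rebuilt |
|---|---|---|---|
| 10 | Null | 0.131-0.162 | 0.144 |
| 10 | Alternative | 0.906-0.939 | 0.922 |
| 5 | Null | 0.132-0.160 | 0.135 |
| 5 | Alternative | 0.794-0.830 | 0.787 |

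The first three agree. The last falls just below the stated range, so power at 5 per cohort is not used below. A separate MCMC calculation at 10 per cohort gave 0.139 and 0.920.

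**2. Share affected, q.** The documents give none. A rough figure comes from the phase I data in protocol 1.2.1.2. SD was the best response in 41 patients and lasted at least 4 cycles (4 × 28 days = 16 weeks) in 26, so 41 − 26 = 15 of 114 evaluable patients (13%) had shorter SD. Of 111 discontinuations, 96 were for progression, leaving 15. The named other reasons sum to 8 + 3 + 1 = 12. So 12/111 to 15/111 (11% to 13.5%) were not for progression. The product is 0.132 × 0.108 = 1.4% to 0.132 × 0.135 = 1.8%, taken as 2%. This multiplies two marginal rates as if independent. Shares of 5% and 10% are assumptions.

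**3. Affected patients dropped, R_g an all-treated rate.** Under the null, the benefit rate among those left is R_g/(1 − q). For lung (R_g 0.45) at q = 10% this is 0.45/0.90 = 0.50, tested against 0.45. Null success rate per cohort, final analysis only, 6000 trials per setting:

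| q | 0% | 2% | 5% | 10% |
|---|---|---|---|---|
| 10 per cohort | 0.144 | 0.166 | 0.203 | 0.284 |
| 5 per cohort | 0.135 | 0.151 | 0.177 | 0.227 |

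With 13-weekly interims and the 10/15 minimums (1500 trials), the 10-per-cohort row becomes 0.151, 0.172, 0.209, 0.283. Coded Y=0 instead, the rate stays at about 0.14.

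**4. R_g an evaluable-only rate.** Dropping these patients leaves the null rate at 0.145-0.147 (10 per cohort). Coding Y=0 multiplies the observed rate by (1 − q): for lung under the alternative at q = 5%, 0.71 × 0.95 = 0.67. Power then falls from 0.922 to 0.901, 0.868 and 0.790 at 2%, 5% and 10%.

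**5. Same data, two codings.** On the all-treated basis at 10 per cohort under the null, the calls differ in 2.2%, 5.9% and 14.0% of cohorts at 2%, 5% and 10%.

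**6. One patient.** Lung with 6 successes, the other seven cohorts at 10 patients each and about their control rates (HNSCC at 4/10): 6/9 gives 0.82, a success, and 6/10 gives 0.75, not a success. Colorectal (R_g 0.38) with no data elsewhere: 5/9 gives 0.83 and 5/10 gives 0.75. With the other seven at control, neither colorectal result passes (0.76 and 0.69).

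All simulated affected patients are SD stoppers without benefit. The confirmed CR/PR group is not quantified.

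**The case against.** A reader might infer that the SAP orders these patients to be excluded and so breaks its own error control. The documents do not support that. Exclusion is one reading. Efficacy is analysed in the FAS, the only stated exclusion is of cohorts under 3 patients, and SAP 4.2 keeps NE as a reported class ("different categories of overall response (e.g., for solid tumor - CR, PR, SD, PD, and NE") in a FAS analysis. The first interim also counts patients who have discontinued. For an SD-only stopper the protocol definition already implies failure.

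The size can also be challenged. The only share that can be built from the documents, about 2%, stays under 0.20. All phase I non-progression stops, at any time and with any response, were 12-15 of 132 treated (9-11%), so 10% is near an upper limit. Inflation also needs R_g to be an all-treated rate, which is not stated. The cohorts and R_g values are examples, and the study is exploratory. The confirmed CR/PR group must be small: the first scan is at week 8, confirmation takes at least 4 more weeks, and phase I had 3 PRs in 114.

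These points limit the size and stand. They do not close the gap. The FAS fixes who is in the set but not Y for a patient whose outcome is declared non-evaluable. NE in SAP 4.2 is a category for ORR, not CBR. The no-imputation rule and the undefined evaluable counts leave room to drop these patients. The basis of R_g decides which error follows, and its absence is part of the problem.

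**Conclusion.** The point holds as an undeclared departure from protocol 10.4.1 on the primary decision, left without a coding in Section 8. It should be fixed, with medium confidence about its size.

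If these patients are dropped and R_g is all-treated, CBR is biased upward. At 10 per cohort the null success rate is 0.16-0.17 at about 2% affected and reaches the stated 0.20 at roughly 5%. If R_g is evaluable-only, the cost falls on power instead, and only under Y=0 coding. A claim that type I error exceeds 0.20 would need a share of 5% or more, exclusion, and an all-treated R_g. The documents establish none of the three.

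The figures rest on the example cohorts and rates and on treating every affected patient as an SD stopper.

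**What to change.** 1. In SAP 4.1 and Section 8, keep all FAS patients of every cohort that qualifies for the model (minimum size met, R_g available) in the primary Bayesian analysis. Code Y=0 for anyone who stops before week 16 without a confirmed CR/PR, whatever the reason.
2. Report the evaluable-only version as a sensitivity analysis.
3. State whether each R_g is an all-treated or an evaluable-only rate, and match it to the coding.
4. State whether these patients count toward the 10 and 15 minimums and the cap of 30.
5. Reconcile confirmed CR/PR before week 16 across protocol 10.4.1 (counts as benefit), Appendix R (benefit assessed at 16 weeks) and SAP 4.1 (non-evaluable after an early non-progression stop).
6. Declare any retained departure in SAP 2.3.

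The cost is SAP wording and one sensitivity table, with no new data. CBR will be slightly lower. If R_g proves to be evaluable-only, Y=0 costs about 2 points of power at 2% affected and 5 points at 5% (10 per cohort), so item 3 should be settled together with item 1. The 30-day limit on deaths in SAP 4.3 and 4.4 concerns DOR and PFS and should be handled separately.
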